3.7.2. Measurement of Fever

Temperatures will be taken by the participant using a digital oral thermometer provided by the research staff. Participants will be instructed to wait 30 minutes after consumption of any fluids before taking their temperature. Consumption of fluids, especially cold,⁶³ can alter oral temperature readings by clinically meaningful amounts for up to 30 minutes,^{63,64} which, if unaddressed, may lead to measurement errors.

Table 1: Schedule of Events

	Time of Assessment										
	Screening (pre-enrolment)	Baseline (Prior to intervention)	Days 1-6	Day 7	Days 8-13	Day 14	Days 15-20	Day 21	Week 4	Week 8	Week 12
Eligibility	✓										
Informed Consent	✓										
Randomization		✓									
Medical History & Current Medications		✓									
Demographics		✓									
Study Intervention			✓	✓	✓	✓	✓	✓			
EQ-VAS			✓	✓	✓	✓	✓	✓			
Symptom Questionnaire			✓	✓	✓	✓	✓	✓			
EQ-5D-5L		✓		✓		✓		✓	✓	✓	✓
Phone Call Follow-Up • Concomitant Medications • Adverse Events • Hospitalizations • Delayed return to usual health				✓		✓		✓	✓	✓	✓

EQ-VAS: EuroQol Visual Assessment Scale; EQ-5D-5L: EuroQol 5-Dimension 5-Level. EQ-VAS and symptom questionnaires must be filled in on the appropriate days. A 3-day window will be allowed for EQ-5D-5L completion and phone call follow-up for the first 4 weeks. The window will increase to 5 days for weeks 8 and 12. Compliance to the intervention will be participant-reported and take place on day 21 or week 4.

Table 2: Outcome Assessment Methods

Objective	Assessment Method
Participant-reported health	EQ-VAS
Health Status	EQ-5D-5L
Symptom severity & duration of COVID-19 symptoms	Internally developed questionnaire
Incidence of delayed return to usual health	Call with participants
Incidence of Hospitalizations, including ER, acute care, and ICU admissions.	Data will be gathered through medical records and through calls with the participant
Length of Stay	
Incidence of Mortality	Data will be gathered through medical records or through obituary searches if medical records are not available

4. Study Conduct

4.1. Ethical Considerations & Study Oversight

Ethical approval for this study will be sought from Research Ethics Boards (REBs) of the Ottawa Health Sciences Network (OHSN) and Canadian College of Naturopathic Medicine (CCNM). Renewals will be submitted and approved annually by each REB. The protocol, informed consent form, recruitment materials, and all participant materials will receive approval from both REBs prior to any participant being enrolled. This trial will also be submitted to both the Natural and Non-Prescription Health Products Directorate (NNHPD) and Therapeutic Products Directorate (TPD) of Health Canada. The trial will be registered on clinicaltrials.gov and updated regularly as per ethical requirements. The trial can be found by searching the NCT number NCT04780061

This study will be conducted according to the Canadian and international standards of Good Clinical Practice (GCP), the Health Canada Food and Drug Act, Part C, Division 5, Drugs for Clinical Trials Involving Human Subjects and Part 4 of Health Canada's Natural and Non-Prescription Health Product Regulations for Clinical Trials.

4.2. Quality Control and Quality Assurance

4.2.1. Monitoring

The trial will have a quality control monitoring process in place to verify that all data are accurate and complete. Site investigators will permit trial-related monitoring, audits and regulatory inspections, and direct access to source data/documents. The monitor will generate a site monitoring report for the site

investigator to detail significant findings, deviations, deficiencies, plausibility, record completeness and any corrective actions to be taken. Full information can be found in the monitoring plan document.

4.2.2. Standard Operating Procedures (SOPs)

The Ottawa Hospital Research Institute (OHRI) and the Centre for Health Innovation (CHI) will follow their individual institutional SOPs. A Procedures Manual, as well as study-specific SOPs, will be developed for study-specific procedures. These documents will be used to facilitate study conduct and training.

4.2.3. Adherence to the Protocol

4.2.3.1. Protocol Amendments

All amendments to this protocol will be reviewed by both REBs and submitted to the NNHPD and the TPD as either a notification or Clinical Trial Application Amendment (CTA-A). Both the principal investigator and qualified investigator will sign the approved protocol prior to implementation, and each investigator and member of the research team will be adequately trained prior to carrying out and study-specific tasks after the approval of the amendment.

4.2.3.2. Protocol Deviations

No deviations from this protocol will be permitted without the prior written approval of the Sponsor, except when the modification is needed to eliminate an immediate hazard or hazards to participants. Any deviations that may affect a participant's treatment or informed consent, especially those increasing potential risks, will receive prior approval from the REB unless performed to remove an immediate safety risk to the participants. In this case they will be reported to the REB immediately thereafter. Any departures from the protocol will be documented in the participant's file.

4.3. Screening and Recruitment

4.3.1. Screening by Clinical Staff

Clinical screening will be facilitated by a clinical team at TOH under the direction of [name], Manager of Patient Safety and Clinical Quality at TOH. Nurses from this team, who are not part of the research team, are responsible for contacting any person who tests positive for COVID-19 at a test centre associated with TOH who does not have access to MyChart or has access but has not reviewed their result in a timely manner. The clinical team will have knowledge if the potential participant is OK to be contacted for research through EPIC (The Ottawa Hospital's electronic medical record system) or will ask this question if no information is entered in EPIC. Nursing staff will notify the trial coordinator of all potentially eligible and interested patients through EPIC. Study staff at the CHI will then contact each patient by phone and further determine their eligibility for the study. If a patient is interested and eligible, they will

be taken through the informed consent process and sign an electronic informed consent form using Adobe Sign.

4.3.2. Screening by Research Staff

Research screening will be done in partnership with The Ottawa Hospital's COVID-19 data warehouse team under the direction of [name]. The data warehouse will generate a list of all patients who test positive for COVID-19 at a test centre associated with TOH. This list will be sent to the research team daily and will function as the equivalent to a clinic's daily appointment list. Research staff will conduct individual chart review to determine if the patient has consent to contact enabled in EPIC, whether they have MyChart enabled, and whether they have reviewed their result. If the patient is marked as "OK to contact," has MyChart enabled and has viewed their result, the research team will contact them about the study. If the patient is interested and eligible, they will be taken through the informed consent process and sign an electronic informed consent form using Adobe Sign.

4.3.3. Community Outreach

Recruitment posters will be put up virtually using the Centre for Health Innovation's website, newsletter, Facebook, LinkedIn, and Instagram. This is an effort to reach patients who have received a positive diagnosis at test centres not associated with TOH.

4.3.4. Consent to Contact via e-mail

Verbal consent will be obtained prior to sending any study materials, including the consent form, or communicating in any way by e-mail. The risks of using e-mail will be discussed with the potential study participant using the template provided by the OHRI. Participants may decline consent to contact via e-mail and receive the consent form and study materials by mail; however, they must comply with the study inclusion criteria to return a signed consent form within 4 days of the onset of their first symptoms.

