3.3. Inclusion/Exclusion Criteria

3.3.1. *Inclusion criteria:*

1. Adults (≥ 18) who test positive for SARS-CoV-2 by reverse transcriptase polymerase chain reaction (RT-PCR) in an outpatient setting
2. Access to internet

3.3.2. *Exclusion criteria*

1. Symptom onset greater than 7 days prior to enrolment
2. Supplementing regularly with >500 mg vitamin C, >1000 units vitamin D, >120 mcg vitamin K (any form), or >15 mg zinc taken daily within the past month
3. Currently taking warfarin or an equivalent vitamin K antagonist anticoagulant
4. End stage chronic kidney disease
5. History of calcium oxalate kidney stones
6. Active granulomatosis (sarcoidosis, tuberculosis, lymphoma)
7. Known hypercalcemia or hypervitaminosis D

8. Currently taking either of the following antibiotics: cephalexin, tetracyclines
9. Known allergy to any investigational product, silicon dioxide, cellulose, or medium chain triglyceride oil
10. Participating in an investigational study or participation in an investigational study within the past 30 days
11. Any reason which, under the discretion of the qualified investigator or delegate, would preclude the patient from participating.

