3.5. Manufacturing & Distribution of Product

Investigational products (including active treatments and placebo) for this study will be manufactured and distributed to participants by Vitazan Herbs and Supplements Inc. Specific formulations of each study product are outlined below.

Specific Product: Vitamin D3 50,000 IU

Formulation: Capsule. Each capsule will contain 500 mg (50,000 units) cholecalciferol (vitamin D3)

Dose: One capsule on day 1 of the intervention period

Placebo Equivalent: microcrystalline cellulose capsule, 350 mg

Absolute Contraindications: history of hypervitaminosis D, hypercalcemia or sarcoidosis

Specific Product: Vitamin K2/D

Formulation: Liquid. Each 0.0285 mL drop contains 30 mcg menaquinone-7 (MK-7, vitamin K2) and 3.125 mcg (125 units) cholecalciferol (vitamin D3).

Dose: 0.114 mL (four drops) twice daily for 21 days totalling 240mcg MK-7 and 1,000 units cholecalciferol per day.

Placebo Equivalent: Medium chain triglyceride oil

Absolute Contraindications: history of hypervitaminosis D, hypercalcemia or sarcoidosis; warfarin or another vitamin K antagonist anticoagulant

Specific Product: Vitamin C/Zinc

Formulation: Capsule. Each capsule will contain 666 mg ascorbic acid (vitamin C) and 8.3 mg of zinc acetate

Dose: Three capsules three times daily for 21 days totalling 6 g ascorbic acid and 75 mg zinc acetate per day.

Placebo Equivalent: microcrystalline cellulose capsule, 350 mg

Absolute Contraindications: calcium oxalate kidney stones, end stage chronic kidney disease, cephalexin, tetracycline antibiotics

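### Section 4.3.4 enforces a 4-day consent limit that the eligibility criteria do not contain, and exclusion 6 bars only active sarcoidosis where section 3.5 sets no such restriction

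*Combined protocol and SAP*

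**What the plan says.** **Consent window.** Section 4.3.4 offers a paper route: "Participants may decline consent to contact via e-mail and receive the consent form and study materials by mail". It then says that these people "must comply with the study inclusion criteria to return a signed consent form within 4 days of the onset of their first symptoms". Section 3.3.1 has two inclusion criteria, an adult with a positive outpatient RT-PCR and internet access. The first exclusion in section 3.3.2 is "Symptom onset greater than 7 days prior to enrolment".

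**Contraindications.** Section 3.5 lists these product by product. The entry for the 50,000-unit vitamin D3 capsule reads "Absolute Contraindications: history of hypervitaminosis D, hypercalcemia or sarcoidosis". For the vitamin K2/D drops the list is "history of hypervitaminosis D, hypercalcemia or sarcoidosis; warfarin or another vitamin K antagonist anticoagulant". In section 3.3.2, exclusion 6 reads "Active granulomatosis (sarcoidosis, tuberculosis, lymphoma", exclusion 7 reads "Known hypercalcemia or hypervitaminosis D", and exclusion 11 allows "Any reason which, under the discretion of the qualified investigator or delegate, would preclude the patient from participating". Section 3.6 sends the reader to both the exclusion list and section 3.5 for absolute contraindications. It stops product for anyone who is put on a contraindicated medicine, or given a contraindicated diagnosis, during the study.

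**The concern.** Both are operative eligibility rules, and screening staff need one answer for each patient.

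(a) Section 4.3.4 relies on an inclusion criterion that does not exist, and its limit conflicts with the one symptom clock that does. Someone eligible under section 3.3 can be turned away under section 4.3.4.

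(b) A person with inactive sarcoidosis has a condition that section 3.5 calls an absolute contraindication, yet no non-discretionary item in section 3.3.2 keeps that person out. If randomised to the active arm, they would be due the 50,000-unit capsule on day 1. That is a single dose, so stopping product later cannot reverse it.

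**Working it through.** The plan gives no figure to reproduce. The check compares texts, with one small calculation.

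**(a) Two limits on two clocks.**

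| | Section 4.3.4 | Exclusion 1 |
|---|---|---|
| Clock starts | onset of first symptoms | symptom onset |
| Clock stops | signed consent returned | enrolment |
| Limit | 4 days | 7 days |
| Applies to | people who decline e-mail | everyone |

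Table 1 places informed consent in the pre-enrolment screening column, so enrolment falls on or after the day consent is returned. Let *g* be the days from return of consent to enrolment. The plan does not give *g*, so it is varied here as an assumption.

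- Latest return day compatible with exclusion 1: 7 − *g*.
- Latest return day under section 4.3.4: 4.
- Return days lost: max(0, 7 − *g* − 4) = max(0, 3 − *g*).

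| *g* (assumed) | Latest return day under exclusion 1 | Days lost |
|---|---|---|
| 0 | 7 | 3 |
| 1 | 6 | 2 |
| 2 | 5 | 1 |
| 3 or more | 4 or earlier | 0 |

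The loss is between 0 and 3 days. It also depends on whether a form counts as returned when posted or when received, which section 4.3.4 leaves open.

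**(b) Section 3.5 against section 3.3.2.** Section 3.5 names 8 distinct absolute contraindications.

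| Section 3.5 | Section 3.3.2 | Comparison |
|---|---|---|
| Vitamin K antagonists | item 3 | matched (current use) |
| End stage kidney disease | item 4 | matched |
| Calcium oxalate stones | item 5 | matched |
| Cephalexin | item 8 | matched (current use) |
| Tetracyclines | item 8 | matched |
| Sarcoidosis | item 6 | narrower: active disease only |
| Hypervitaminosis D | item 7 | no mismatch shown |
| Hypercalcemia | item 7 | no mismatch shown |

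Count: 5 matched + 1 narrower + 2 with no mismatch shown = 8.

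*Sarcoidosis.* If the words about history in section 3.5 govern the whole list, past disease is contraindicated. If they govern only the first item, sarcoidosis stands unqualified. On neither reading is it limited to active disease, as it is in exclusion 6.

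*Exclusion 7.* Hypervitaminosis D directly follows the words about history in section 3.5, so how far those words reach matters only for hypercalcemia. For both conditions, a documented past episode can fairly be called known. The wording could be clearer, but an error is not shown.

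*Whether another rule closes the sarcoidosis gap.* The section 3.6 stopping rule needs a new medicine or a new diagnosis, and long-standing inactive disease is neither. Table 1 collects medical history at baseline, which could bring the condition to light, but section 3.3.2 would not then exclude the person. Exclusion 11 could, at the investigator's discretion.

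**The case against.** **On (a).** Four days may be a deliberate allowance for postal delay, and with a gap of 3 days or more it costs nothing beyond exclusion 1. That may be so, but the section presents the limit as an existing inclusion criterion, and there is none. A reader might infer that all participants are held to 4 days, or that 3 of the 8 permitted days (0 to 7) are always lost. Neither is supported. The sentence is written for people who decline e-mail, while sections 4.3.1 and 4.3.2 use electronic signature. The 3-day figure holds only if enrolment follows on the day consent is returned.

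**On (b).** Sections 3.3.2 and 3.5 can be read cumulatively, so that either list bars use. Section 3.4 refers the reader to section 3.5 for contraindications, and calling a condition an absolute contraindication is itself a direction not to give the product. This stands: it would be too strong to say that nothing in the plan tells staff to withhold it. But on that reading a person with inactive sarcoidosis can be randomised to a regimen that includes products they must not take, and the plan does not say what happens next. The procedures manual and study-specific procedures planned in section 4.2.2 may settle it, but they are not part of these documents.

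A reader might also infer that the day-1 dose would harm someone with inactive sarcoidosis. The documents do not show that, and active disease may be all the sponsor meant to exclude.

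**Conclusion.** Both conflicts are present as written, and both are minor.

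(a) The 4-day limit in section 4.3.4 has no basis in section 3.3.1 and can refuse mail-route patients whom exclusion 1 admits. The cost is 0 to 3 days of the consent window, depending on the gap between return of consent and enrolment. The documents do not show which limit was intended.

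(b) Exclusion 6 is narrower than section 3.5 for sarcoidosis, and for sarcoidosis only.

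The documents give no counts. The judgement that few people are affected assumes that declining e-mail and having inactive sarcoidosis are both uncommon among those screened. With 1:1 allocation, about half of any such sarcoidosis patients would receive placebo.

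A reader might suspect an effect on the trial's result. The documents do not support one: these rules act before allocation and apply to both arms alike, so they do not bias the comparison, and neither the power calculation nor the analysis depends on them.

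**What to change.** **Section 4.3.4.** Replace the 4-day clause with a reference to exclusion 1: signed consent must be received in time to enrol within 7 days of symptom onset. If a shorter postal deadline is wanted, state it as a mail-route rule, not as an inclusion criterion.

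**Exclusion 6.** Reword as: *history of sarcoidosis, or other active granulomatosis (tuberculosis, lymphoma)*. If the sponsor judges inactive sarcoidosis safe, amend section 3.5 instead to read *active sarcoidosis* for both vitamin D products, with the reason. Either choice makes the two lists agree on sarcoidosis.

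**Optional.** Exclusion 7 could read *known or history of* the two conditions. This is a clarification only.

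**Cost.** Two wording edits, or three with the option, in one amendment submitted as section 4.2.3.1 requires, plus matching changes to any screening form that repeats the wording. A few more mail-route patients may be admitted, and a few people with past sarcoidosis excluded if exclusion 6 is widened. The sample size and analysis do not change.

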4.4. Informed Consent

All participants for this study will be provided a consent form describing this study and providing sufficient information for participants to make an informed decision about their participation in this study. Each participant will have sufficient opportunity to discuss the study, have all their questions addressed and consider the information in the consent process prior to agreeing to participate. Participants may withdraw consent at any time during the study. This consent form will be signed and dated by the participant, and the investigator and/or designated research professional obtaining the consent. The original signed informed consent form will be retained in the participant's study files and a copy will be provided to the participant.

4.5. Randomization, Blinding, and Control

Participants will be randomized in a 1:1 ratio using a web-based tool provided and maintained by an independent statistician at the Ottawa Methods Centre. Randomization will be based on mixed block sizes of 4 and 6 to ensure adequate balance at all stages of recruitment.

All products will have an equivalent placebo such that each product and pill bottle are both indistinguishable from the treatment, except for the lot number, which will allow Vitazan to distinguish between treatment and placebo. Study participants and research staff will remain blinded for the duration of the study until recruitment is finished and all analyses are completed. The Data Safety and Monitoring Board (DSMB) may request that participants be unblinded if they are concerned about participant safety (e.g., due to the distribution of adverse events). In this case, the PI and QI will be notified of the unblinding and this will be documented and stored in the study binder.

Compliance to the study protocol will be participant-reported during the weekly calls by the research staff. Participants will be instructed to return all partially used and unused investigational products to the CHI or their local pharmacy for destruction. All efforts will be made to ensure participants start the study product as soon as possible after enrolment and randomization. Days from symptom onset to starting the study product will be monitored and compared between arms to ensure consistency.

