3.4. Interventions

The interventions for this study will consist of dietary supplements for participants in the treatment arm and a placebo for those in the control arm. Three vitamins and one mineral will be included in the intervention for those in the treatment arm – vitamin D3, vitamin C, vitamin K2, and zinc. Upon enrolment and randomization, participants will be provided either dietary supplements or placebo by the study staff. Study interventions are to be started as soon as possible after enrolment and randomization and will continue for 21 days. Participants will be responsible for taking their doses and will be required to return all unused study product to the CHI or their local pharmacy to be properly destroyed. Phone calls will be made to participants at weeks 1, 2, 3, and 4 post-enrolment to check in and inquire about compliance and potential side effects.

All pill bottles will bear labels that comply with Health Canada Regulations. These labels will be in both official languages and contain the expiry date, storage conditions, lot number and the name and address of the manufacturer. An additional statement will be added to each label indicating that it is an investigational product to be used only by a qualified investigator, the trial's sponsor name and address, and protocol code. All study products will be packaged in sealed bottles. Participants will be instructed to store all products as indicated on the product label in a location that is out of reach of children and not to use if the seal is broken. Product accountability records will be maintained to track dispensation, returns and destruction of the study product, and will be maintained by the study staff at the Centre for Health Innovation (CHI). Product inventory will be stored as indicated on the label with daily temperature monitoring.

Information regarding all investigational products, including dosing, timing, absolute contraindications and rationale for use, is summarized below and in section 3.5.

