4.6. Setting

This study will take place in Ottawa and will involve personnel from the Centre for Health Innovation and The Ottawa Hospital & Ottawa Hospital Research Institute. Day-to-day study activities, including screening & recruitment, outcome collection & follow-up, and product dispensing & tracking, will be managed by study staff at the CHI under the supervision of the principal investigator. The principal investigator will communicate regularly with the qualified investigator and other members of the research team to ensure proper trial conduct. Study interventions will be taken at home by study participants.

5. Sample Size Determination and Power Calculation

With respect to the primary outcome of participant-reported overall health, power calculations were conducted based on between-group differences at a single time point (21 days) and Cohen's guideline for a small effect size of 0.3. A sample size of 176 (88 per arm) provides 80% power to detect a difference at an α of 0.05. To account for an approximate 10-15% lost to follow-up we will enrol 200 participants (100 per arm).

6. Data Collection, Analysis, and Management

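### The lot number on every bottle label differs by arm, so staff who track product can see who shares a lot, and one code break can expose more than one participant

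*Combined protocol and SAP*

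**What the plan says.** Four parts of the protocol bear on this.

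- **The mark.** Section 4.5 describes placebo and active products and bottles as indistinguishable "except for the lot number, which will allow Vitazan to distinguish between treatment and placebo". The lot number is the only difference it names.
- **Where it appears.** Under section 3.4, bottle labels must "contain the expiry date, storage conditions, lot number and the name and address of the manufacturer".
- **Who handles it.** Section 4.6 says that screening and recruitment, "outcome collection & follow-up, and product dispensing & tracking, will be managed by study staff at the CHI". Section 3.4 says that "participants will be provided either dietary supplements or placebo by the study staff", and gives CHI staff the records of dispensing, returns and destruction. Unused product goes back to the CHI or to a local pharmacy (sections 3.4 and 4.5). Section 3.5, however, says that product is "manufactured and distributed to participants by Vitazan Herbs and Supplements Inc".
- **Code breaks.** Section 4.5 keeps participants and research staff blinded until analyses are complete, but lets the DSMB ask for unblinding. It adds: "In this case, the PI and QI will be notified of the unblinding".

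Randomisation is 1:1 in blocks of 4 and 6, through a web tool kept by an independent statistician (section 4.5). Planned enrolment is 200, 100 per arm (section 5). The documents describe no participant-specific kit number, no masked or shared lot code, no separate unblinded dispenser, and no rule that limits a code break to one person. They do not say how many lots each arm will have.

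**The concern.** A mark that differs by arm and is shared by many participants links their blinding together. Staff do not need the key to see the groups; the labels and accountability records show them. Two things are then at risk.

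**Blinding.** If one participant's arm becomes known to someone who can see lot numbers, everyone on that lot is exposed too. CHI staff ask about adverse events each week (section 7.2) and assess delayed return to usual health by phone (section 3.7). Gastrointestinal events are expected with the active products (section 7.3). COVID-19 also causes them, so a single report says little, but reports grouped by lot could hint at which lot is active.

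**Allocation concealment.** The group that can see past lots also manages recruitment, the block sizes are in the protocol, and exclusion criterion 11 (section 3.3.2) is discretionary. Being able to predict the next lot group weakens concealment.

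**Working it through.** The plan gives no figure on this point, so there is none to reproduce. The checks below measure what the stated design would allow.

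**1. Exposure from one code break**

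Input: 100 participants per arm (section 5). Assumption: K equal lots per arm, since K is not stated. Participants on the broken lot = 100 / K, counting the person unblinded.

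| Lots per arm (K) | Participants exposed | Share of 200 |
|---|---|---|
| 1 | 200 (100 on that lot; the other lot must be the other arm) | 100% |
| 2 | 100/2 = 50 | 25% |
| 5 | 100/5 = 20 | 10% |
| 10 | 100/10 = 10 | 5% |
| Unique kit number, no arm mark | 1 | 0.5% |

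**2. Predicting the next lot group**

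Inputs: 1:1 allocation in blocks of 4 and 6 (section 4.5). Assumptions: the two block sizes are equally likely, lots separate the participants into two recognisable groups, and the observer has seen every earlier lot in order. The observer always names the group with fewer allocations so far. For a block of size 2b, the expected number of correct guesses is

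b + (2^(2b) / C(2b, b) − 1) / 2.

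- Block of 4 (b = 2): 2 + (16/6 − 1)/2 = 2.833, and 2.833/4 = 70.8%.
- Block of 6 (b = 3): 3 + (64/20 − 1)/2 = 4.1, and 4.1/6 = 68.3%.
- Mixed: (2.833 + 4.1)/(4 + 6) = 69.3%, against 50% by chance.

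A simulation of 1,500 lists of 200, with a guesser who updates on each allocation but does not know where blocks begin or end, gave 69.2% correct. About 5.5% of allocations were known with certainty. Over 200 participants, 0.693 × 200 is about 139 correct guesses, against 100 by chance. These are guesses of the lot group, not of the treatment.

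**3. Who sees the labels**

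Sections 3.4 and 4.6 put dispensing with study staff; section 3.5 puts distribution to participants with the manufacturer. Both cannot describe the same step. If the manufacturer ships direct, staff would see fewer labels at dispensing. The accountability records and the returned product would still come to the CHI.

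**4. Capsule match (separate)**

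Section 3.5 states 666 + 8.3 = 674.3 mg of content in each active vitamin C/zinc capsule. For the placebo it states "Placebo Equivalent: microcrystalline cellulose capsule, 350 mg". At nine capsules a day for 21 days (9 × 21 = 189), this would be 189 × 674.3 mg = 127.4 g against 189 × 350 mg = 66.2 g. That holds only if 350 mg is the full fill weight, and it leaves out shells, excipients and the bottle.

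**The case against.** The other side has a good deal to say, and much of it limits the point.

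- **A reader might infer that one unblinding decodes the whole trial.** That needs one lot per arm, which the documents do not state. With more lots the exposure is partial.
- **A reader might infer that the principal and qualified investigators learn the arm.** Section 4.5 says only that they are notified of the unblinding. It does not say that they are told the arm or that anyone links it to a lot. The manufacturer is the only party said to read the code.
- **A reader might infer that staff could steer patients to active treatment.** The 69% predicts the lot group. Knowing which group is active needs a code break or a clue such as side effects.
- **A reader might infer a direct bias in the primary outcome.** The EQ-VAS is completed daily by participants themselves. Each sees only their own label and has no key, and nothing describes staff influencing the scores. Hospitalisation comes from medical records where possible (sections 3.6.1 and 3.7), with calls as a further source.
- **The same individuals need not do every task.** Section 4.6 speaks of staff at the CHI as a group.
- **The capsule weights may mean nothing.** The same 350 mg placebo is listed against the vitamin D capsule, so it may be a generic description, and section 4.5 says that the products are indistinguishable.

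All of these stand as limits on size. None removes the core: an arm-level mark on every label, handled by the group that recruits and collects outcomes, with no participant-level code described. An intention to keep staff blinded does not replace a labelling scheme that secures it.

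**Conclusion.** The point holds as a weakness in blinding and concealment that is cheap to remove. It does not show that the blind will be broken. One code break, if its result reaches someone who can see lot numbers, exposes between 10 participants (ten equal lots per arm) and all 200 (one lot per arm), over the range examined. The next lot group is predictable about 69% of the time, given equally likely block sizes, lots that visibly separate the arms, and sight of every earlier lot in order. How much staff see at dispensing depends on reconciling section 3.5 with sections 3.4 and 4.6; records and returns leave some exposure either way. The capsule weights are a matter to confirm and establish no mismatch.

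**What to change.** Before packaging:

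1. Label each participant's set with a unique kit number assigned by the web randomisation tool.
2. Put no arm-identifying mark on anything that staff or participants see. A common or masked packaging lot code would do this where labelling rules allow; that needs checking with the regulator, because section 3.4 requires a lot number on the label.
3. Keep the kit-to-arm list only with the manufacturer and the independent statistician, and state in section 4.5 what a code break discloses, and to whom. One break then reveals 1 of 200 (0.5%), and the label says nothing about the next allocation.
4. Reconcile section 3.5 with sections 3.4 and 4.6 on who sends product to participants.
5. Confirm that the 350 mg placebo capsule matches the active vitamin C/zinc capsule in size and weight.

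The cost of items 1 to 3 is a kit list and changed labels, with no extra participants. Item 4 is an edit. Item 5 costs nothing if the capsules already match, and otherwise the cost of matching the placebo.
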